### Study treatment start and end date

**Study treatment start date** is defined as the first date when a non-zero dose of study drug is administered and recorded on the Drug Administration Record (DAR) CRF page.

**Study treatment end date** is defined as the last date when a non-zero dose of study drug is administered and recorded on the DAR CRF page of the core study.

### Study day

Study day will be calculated as (event date – study drug start date + 1 day) for events that occurred on or after study drug start date (e.g. visit, lab samples, AEs). For events prior to study drug start date (e.g., time of diagnosis), study day will be negative and calculated as (event date – study drug start date). Note that study drug start date is study day 1 and the day before study drug start date is study day -1 (i.e. no study day 0).

Due to the study drug dosing schedule, one month will be considered as 28 days. However, for "time since event" data (e.g., medical history), one month will be considered as 365.25/12 days for events that occurred prior to study Day 1.

### Baseline and post-baseline definitions

In general, a baseline value refers to the last measurement available prior to administration of the first dose of study treatment. A post-baseline value refers to a measurement taken after the first dose of study treatment.

For Treatment Period 2, Week 16 assessments will be considered the baseline for all analyses performed during this period.

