4.1 Inclusion Criteria

Patients/subjects eligible for inclusion in this study must fulfill all of the following criteria:

1. Patient must be able to understand and communicate with the investigator and comply with the requirements of the study and must give a written, signed and dated informed consent before any study assessment is performed
2. Male or non-pregnant, non-lactating female patients at least 18 years of age

3. Diagnosis of moderate to severe AS with prior documented radiologic evidence (x-ray or radiologist's report) fulfilling the Modified New York criteria for AS [REDACTED]
4. Active AS assessed by total BASDAI of ≥ 4 (NRS of 0-10) at baseline
5. Spinal pain as measured by BASDAI question #2 of ≥ 4 (NRS of 0-10) at baseline
6. Total back pain of ≥ 4 on a NRS of 0-10 at baseline
7. Patients should have been on NSAIDs at the maximum tolerated dose for at least 4 weeks prior to their Baseline Visit, with an inadequate response or for less than 4 weeks if withdrawn for intolerance, toxicity or contraindications
8. Patients who are regularly taking NSAIDs (including COX-1 or COX-2 inhibitors) as part of their AS therapy are required to be on a stable dose for at least 2 weeks before their Baseline Visit
9. Patients who have been on a TNF α inhibitor (not more than one) must have experienced an inadequate response to previous or current treatment given at an approved dose for at least 3 months prior to baseline or had been intolerant upon administration of an anti-TNF α agent
10. Patients who have previously been on a TNF α inhibitor will be allowed entry into study after appropriate wash-out period prior to their Baseline Visit:
 - 4 weeks for Enbrel® (etanercept) – with a terminal half-life of 102 ± 30 hours (s.c. route)
 - 8 weeks for Remicade (infliximab) – with a terminal half-life of 8.0-9.5 days (i.v. infusion)
 - 11 weeks for Humira (adalimumab) – with a terminal half-life of 10-20 days (average 2 weeks)(s.c. route)
 - 11 weeks for Simponi (golimumab) – with a terminal half-life of 11-14 days
 - 11 weeks for Cimzia (certolizumab) – with a terminal half-life of 14 days
11. Patients taking MTX (≤ 25 mg/week), sulfasalazine (≤ 3 g/day), or leflunomide (≤ 20 mg/day) are allowed to continue their medication and must have taken it for at least 2 months and have to be on a stable dose for at least 4 weeks prior to baseline
12. Patients on MTX must be on a stable folic acid supplementation before their Baseline Visit.

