6.5.2.1 ASAS Responder Criteria 20% (ASAS20)

ASAS 20 response is defined as an improvement of $\geq 20\%$ and ≥ 1 unit on a scale of 10 in at least three of the four domains and no worsening of $\geq 20\%$ and ≥ 1 unit on a scale of 10 in the remaining domain. Assessments will be made relative to patient’s baseline values.

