6.5.2.2 ASAS Responder Criteria 40% (ASAS40)

ASAS 40 response is defined as an improvement of $\geq 40\%$ and ≥ 2 units on a scale of 10 in at least three of the four domains and no worsening at all in the remaining domain. Assessments will be made relative to patient’s baseline values.

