8.5 Adjudication committee

Not required.

9 Data analysis

It is planned that the data from all centers that participate in this protocol will be combined, so that an adequate number of patients will be available for analysis.

The analysis will be conducted on all patient data at the time the trial ends.

Any data analysis carried out independently by the investigator should be submitted to Novartis before publication or presentation.

Upon completion of Treatment Period 1 (Week 16), responders will enter Treatment Period 2 and continue to receive secukinumab 150mg every 4 weeks through Week 48. Inadequate responders will enter Treatment Period 2 and will be randomized (1:1, double-blinded) to secukinumab 300 mg or secukinumab 150 mg every 4 weeks through Week 48. Nonresponders will be discontinued from the study at Week 16.

Efficacy, safety, and other data from Treatment Period 1, randomized Treatment Period 2 for inadequate responders, and blinded Treatment Period 2 for responders will be summarized. For continuous variables, summary statistics (mean, standard deviation, median, 25th and 75th percentiles, interquartile range, minimum, and maximum) at each time point and for change from baseline to Week 16, and change from Week 16 to each time point by treatment group will be reported. For discrete variables, frequency counts and percentages at each time point will be reported by treatment group.

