9.4.2 Statistical model, hypothesis, and method of analysis

Let π_j denote the probability of an ASDAS inactive disease at Week 52 for treatment group j , $j = 1, 2$, where 1 and 2 correspond to secukinumab 150 mg and secukinumab 300 mg, respectively. Accordingly, $\pi_j/(1 - \pi_j)$ is the odds for treatment group j , $j = 1, 2$.

The primary efficacy variable will be analyzed at each time point using a logistic regression model with treatment, TNF-alpha inhibitor status (naive, inadequate responder), and baseline body weight as explanatory variables (Stokes, Davis, and Koch, 2012). The odds ratios and 95% confidence intervals for the odds ratios will be reported, based on the fitted model.

The primary analysis of the primary efficacy variable will be based on the Full Analysis Set.

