9.4.4 Sensitivity analyses

A 95% confidence interval for the difference between the two treatment groups in the proportion of patients who have ASDAS inactive disease will be calculated using the normal approximation to the binomial distribution for the Full Analysis Set.

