9.5 Analysis of secondary variables

9.5.1 Efficacy variables

The secondary efficacy variables are the following:

1. Reduction in ASDAS ≥ 1.1 from Week 16 (yes, no)
2. Change from Week 16 in total BASDAI
3. BASDAI50 response (yes, no)
4. ASAS20 response (yes, no)
5. ASAS40 response (yes, no)
6. ASAS partial remission (yes, no)
7. Change from Week 16 in ASAS-Health Index
8. Change from Week 16 in FACIT-Fatigue

Analyses of secondary efficacy variables 1 and 3 – 6 at each time point will be similar to the primary and sensitivity analyses of the primary efficacy variable.

Secondary efficacy variables 2, 7, and 8 will be analyzed at each time point by an analysis of covariance model with treatment, Week 16 value, TNF-alpha inhibitor status (naive, inadequate responder), and baseline body weight as explanatory variables. The least squares means of the treatment groups, least squares mean difference, and 95% confidence interval for the difference will be reported, based on the fitted linear model. Missing data will be imputed using the last-observation-carried-forward method. In an additional analysis, missing data will be imputed using multiple imputation.

Analyses of the secondary efficacy variables will be based on the Full Analysis Set.

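### On its most natural reading, the SAP models ASAS20 and ASAS40 from Week 16 instead of the protocol's baseline, and Section 4 does not declare it

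*SAP*

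**What the plan says.** **Protocol.** The ASAS20 definition (6.5.2.1) closes by saying that worsening is judged "on a scale of 10 in the remaining domain. Assessments will be made relative to" the patient's baseline values. The ASAS40 definition (6.5.2.2) closes the same way: "no worsening at all in the remaining domain. Assessments will be made relative to" baseline. Section 9.5.1 says that the analyses of secondary variables 1 and 3 to 6, which include ASAS20 and ASAS40, "will be similar to the primary and sensitivity analyses of the primary efficacy variable". Two results carry over from the primary variable:

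- the logistic model of 9.4.2: "The odds ratios and 95% confidence intervals for the odds ratios will be reported, based on the fitted model";
- the interval for the difference in proportions of 9.4.4, which "will be calculated using the normal approximation to the binomial distribution".

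**SAP.** Section 2.1.1 first defines baseline in general as the last measurement before the first dose. It then adds: "For Treatment Period 2, Week 16 assessments will be considered the baseline for all analyses performed during this period". Section 2.7.2 models ASAS20 and ASAS40 in the same way as the ASDAS reduction of at least 1.1, that is, by logistic regression and a difference interval at each Treatment Period 2 visit. Responses derived from Week 0 appear in 2.7.2 only among the additional analyses: numbers and percentages (item 2) and line plots (item 3). Section 2.11.2 repeats the protocol's ASAS definitions, including the word baseline, without naming a week. Section 4, which lists departures from the protocol, says nothing about the ASAS reference point.

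**The concern.** A responder endpoint is defined by its reference point as much as by its threshold. Everyone randomised has already improved on 16 weeks of open-label treatment. Response counted from Week 0 asks whether the patient is well improved since entry. Response counted from Week 16 asks whether the patient gained a further 20% or 40% after randomisation. Both are reasonable questions, but they are different events.

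If the models run on the Week 16 version, the odds ratios and intervals that the protocol promised for ASAS20 and ASAS40 will be reported for another event under the same labels. The protocol-defined event will have no adjusted estimate. A reader who checks Section 4 for departures will not learn that this happened.

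**Working it through.** **1. What the protocol means by baseline.** Protocol Section 9 asks for summaries of "change from baseline to Week 16, and change from Week 16 to each time point by treatment group", so baseline and Week 16 are separate reference points. The list in 9.5.1 attaches Week 16 to variables 1, 2, 7 and 8 and not to ASAS20 or ASAS40. The protocol's reference for these two is therefore Week 0.

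**2. Which reference the SAP models use.** Three things point to Week 16.

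- The rule in SAP 2.1.1 covers all analyses in Treatment Period 2.
- SAP 2.7.2 sets up a separate, additional derivation from Week 0, which would be largely redundant if the modelled responses already used Week 0.
- The covariate moved too: the protocol's baseline body weight became Week 16 body weight in SAP 2.5.2 and 2.7.2, although the code in SAP 5.4.1 still names baseline weight.

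**3. The plan's own figure.** No sample size is given for ASAS20 or ASAS40. The figure for the primary variable reproduces: n = 1.96² × (0.20 × 0.80 + 0.10 × 0.90) / 0.10² = 96.04, rounded up to the stated 97 per arm. It does not depend on the ASAS reference point.

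**4. How far the two events differ.** From the definitions, the highest Week 52 domain score that counts as improved is:

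- ASAS20: min(0.8 × ref, ref − 1)
- ASAS40: min(0.6 × ref, ref − 2)

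| Reference score | ASAS20 | ASAS40 |
|---|---|---|
| 7 | 5.6 | 4.2 |
| 4 | 3 | 2 |
| 3 | 2 | 1 |
| 2 | 1 | 0 |
| 1 | 0 | not attainable |

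Inclusion criterion 6 requires total back pain of at least 4 "on a NRS of 0-10 at baseline". From Week 0 that domain can therefore always meet both criteria (4 to 2 is 50% and 2 units). At Week 16 there is no such floor, and a domain below 2 cannot count towards ASAS40.

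**5. Illustrative patients who would be randomised.** The assumptions are equal scores on all ASDAS inputs and ASAS domains, Week 12 equal to Week 16, and the CRP values shown. The formula in SAP 2.11.1 then becomes ASDAS = 0.36 × score + 0.58 × ln(CRP + 1), because 0.12 + 0.06 + 0.11 + 0.07 = 0.36.

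- *Patient A*: scores 7, 3, 3 at Weeks 0, 16, 52; CRP 10 then 3 mg/L. ASDAS falls from 2.52 + 0.58 × ln 11 = 3.91 to 1.08 + 0.58 × ln 4 = 1.88. From Week 0 the change is 4 units, or 57%: ASAS20 and ASAS40 are both met. From Week 16 the change is zero: neither is met.
- *Patient B*: scores 7 then 1; CRP 10 then 5 mg/L. ASDAS falls from 3.91 to 0.36 + 0.58 × ln 6 = 1.40. If scores stay at 1 or fall to 0 by Week 52, ASAS40 is met from Week 0 and impossible from Week 16. ASAS20 from Week 16 needs a score of 0 in at least three domains. At a score of 1, any CRP above exp((1.3 − 0.36)/0.58) − 1 = 4.06 mg/L keeps ASDAS at or above 1.3.

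Both patients improve and stay at or above 1.3, so both are inadequate responders. The references do not always disagree: scores of 7, 6, 3 meet both criteria from either week.

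**The case against.** The best counter-argument is that no departure is established. SAP 2.11.2 repeats the protocol's endpoint definitions, and an endpoint-specific definition can be read as overriding a general convention. The Week 0 item in 2.7.2 is also loosely drafted: it covers variables 3 to 6, and ASAS partial remission is an absolute state with no reference point, so the contrast with the modelled analyses is weaker evidence than it first appears. This keeps the Week 0 reading possible, and the conclusion is worded accordingly. It does not remove the problem. On that reading 2.11.2 conflicts with the rule for all analyses in 2.1.1, and a programmer cannot tell which event to model.

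The second argument concerns weight, and most of it stands. These are secondary endpoints in an estimation study with no key secondary endpoint. Both reference points are visible in the SAP. An unadjusted Week 0 difference and its interval could be computed from the planned counts, so the main loss is the adjusted odds ratio. The illustrative patients show that the definitions can disagree, not that the 300 mg versus 150 mg contrast would move. The back pain floor covers one of four domains.

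The third argument is that promoting the Week 0 analysis reorders the SAP after database lock. The post-lock entry in the document history names 2.7.2 but not 2.1.1, so the Week 16 convention is not recorded as a post-lock edit. However, the Week 0 reference was set in the protocol, so restoring it is not a choice made after seeing data. The timing should still be stated.

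**Conclusion.** The concern holds. On the most natural reading, the SAP applies the protocol's model and difference interval to ASAS20 and ASAS40 scored from Week 16, leaves the protocol-defined versions with descriptive output only, and does not record the change in Section 4. On the alternative reading, the SAP contradicts itself about the reference week. Either way the text needs correcting.

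The effect is confined to two secondary endpoints. The worked patients rest on assumed scores and CRP values and show only that the two events differ. The share of patients reclassified, and any effect on the treatment contrast, cannot be derived from the documents. The primary endpoint, the sample size and the validity of the randomised comparison are unaffected.

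BASDAI50 has the same unnamed reference in SAP 2.11.6, but the readable protocol gives it no reference point. For that endpoint this is a clarification within the SAP and not a conflict with the protocol.

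**What to change.** - Run the logistic model of Protocol 9.4.2 and the difference interval of 9.4.4 for ASAS20 and ASAS40 scored from Week 0, and present them as the protocol-defined secondary analyses. State that the SAP wording on the Week 0 derivation was added after database lock (document history, 08-Jul-2021).
- Keep the Week 16 version as a clearly labelled additional analysis and declare it in SAP Section 4.
- Name the reference week in SAP 2.7.2, 2.11.2 and 2.11.6, including for BASDAI50 as a clarification.

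The cost is SAP wording and a few model runs. The Week 0 responses are already due to be derived for the planned tables and figures, and no new data are needed.

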### Treatment Period

There are 2 treatment periods for this study defined as:

Treatment Period 1 is defined as the 16-week open-label treatment period starting from baseline until Week 16.

Treatment Period 2 is a 36-week, double-blind treatment period starting from Week 16 until Week 52.

### Lost to follow up

Patients whose study completion status is unclear because they fail to appear for study visits without stating an intention to withdraw.

### On-treatment period

The period where the patients are exposed to the study treatment. For this study the treatment phase consists of 52 weeks.

[figure not shown]
### 2.1.2 Visits windows

*Visit-windows* will be used for the data that is summarized by visit; they are based on the study evaluation schedule and comprise a set of days around the nominal visit day. For any assessment, there are the protocol defined scheduled visits around which visit windows were created to cover the complete range of days within the study. The visit windows are shown in [REDACTED]. These apply to measurements taken at every visit.

For assessments collected less often different visit windows will be applied as detailed below.

When visit windows are used, all visits will be re-aligned, i.e., they will be mapped into one of the visit windows. E.g., if the *Week 4* visit of a subject is delayed and occurs on Day 46 instead of on Day 29, say, it will be re-aligned to visit window *Week 8*. In the case of major deviations from the visit schedule, or due to unscheduled visits, several assessments of a subject may fall in a particular visit window (either scheduled or unscheduled). Statistical approaches to handle multiple assessments in a given visit window are specified in [REDACTED].

Of note, subjects are allowed to have gaps in visits.

[figure not shown]
For data which are **not** collected at every visit (e.g., ASAS-HI, [REDACTED], visit windows defined in [REDACTED] will be combined. For example, if an assessment is at Week 12 and Week 24 only, Week 12 visit window will extend from Day 2 to Day 99 (combining Week 1 to Week 12 visit windows), Week 24 will extend from Day 100 to Day 183 (combining Week 16 to Week 24). If more than one assessment falls into the interval, the rules defined in [Section 2.1.3](#) below are applied.

[figure not shown]
### 2.1.3 Multiple assessments within visit windows

When there are *multiple assessments* in a particular visit window, the following rules are applied to select one value “representing” the subject in summary statistics in a visit window (See [REDACTED]

For baseline assessment definition see [Section 2.1.1](#). For post-baseline visit windows the following applies (unless otherwise specified):

- for *quantitative variables*, the *closest* to the actual visit is chosen (if two assessments have the same distance, then the earlier one will be chosen);
- for *qualitative variables*, the *worst* record is selected. It is noted that in the analyses performed, *worst* case is always well defined.
- in cases where qualitative variables are derived from quantitative variables (e.g., ASDAS, BASDAI50, ASAS20, ASAS40, ASAS partial remission, and reduction in ASDAS $\geq$ 1.1 from Week 16), the visit will be assigned to the quantitative variable, and this visit will be used for the derived qualitative variable.

## 2.2 Analysis sets

The following analysis sets will be used for the statistical reporting and analyses:

**Enrolled Set:** The Enrolled Set consists of all enrolled patients for the initial 16-week, Treatment Period 1.

Note: For safety analyses, the Enrolled Set will consist of enrolled patients for the initial 16-week, Treatment Period 1 who received at least one dose of the open-label treatment, secukinumab 150 mg.

**Responder Set:** The Responder Set consists of all patients who are labeled as responders at the end of Treatment Period 1, and enter Treatment Period 2 receiving blinded secukinumab 150 mg every 4 weeks through Week 48.

**Safety Set:** The Safety Set includes all patients who received at least one dose of study treatment during Treatment Period 2. Patients will be analyzed according to the study treatment received.

**Full Analysis Set:** The Full Analysis Set comprises all patients to whom study treatment has been assigned by randomization. According to the intent-to-treat principle, patients will be analyzed according to the treatment they have been assigned to during the randomization procedure.

**Non-responder Set:** The Non responder Set consists of all patients who are labeled as non-responders at the end of Treatment Period 1 and do not enter Treatment Period 2.

### **2.2.1 Subgroup of interest**

Subgroup analyses will be performed for all the efficacy variables based on the TNF-alpha inhibitor status (naive, inadequate responder).

## **2.3 Patient disposition, demographics and other baseline characteristics**

Summary statistics will be presented for continuous demographic and baseline characteristics and the number and percentage of patients in each category will be presented for categorical variables for each treatment group. The summaries will be reported for Enrolled Set, Responder Set, Safety Set, Full Analysis Set (FAS), and Nonresponder Set.

### **2.3.1 Patient disposition**

The number and percentage of patients screened, completed Treatment period 1 and 2, discontinued Treatment Period 1 or 2 including a summary of reasons for discontinuations will be presented for Enrolled Set and Full Analysis Set. In addition, the reasons for screen failures will be provided.

All patient disposition data will be listed.

Number and percentage of patients with pandemic related protocol deviations will be tabulated for each treatment period. The pandemic period is considered to be a period starting from 1st March 2020 onwards.

### **2.3.2 Patient demographic and other baseline characteristics**

Demographic and other baseline data, including disease characteristics will be listed and summarized descriptively for the Enrolled Set, Responder Set, and by treatment group for Full Analysis Set, Safety Set and Nonresponder Set.

The following demographic and baseline variables, if collected, will be summarized:

#### Continuous variables:

- Age (which is derived from date of birth and the screening assessment date)
- Height (cm)
- Weight (kg)
- BMI (kg/m^2)

#### Categorical variables:

- Sex
- Race
- Ethnicity
- Child-bearing status (for females only) Age (<65 and >=65)

Smoking status at Baseline will be summarized.

In addition to this, data for tuberculosis risk assessment, ECG evaluation and chest X-ray or MRI, as collected from respective CRF pages at Screening Visit 2, will be summarized.

